#### **7.2.5. Blood and CSF for Culture**

Blood and CSF will be sampled up to 6 hours after each IMP dose and held for potential culture (including the dosimetry dose in Part 1). Samples will be cultured only if body temperature is elevated (defined as  $\geq 38^{\circ}\text{C}$  [ $\approx 100^{\circ}\text{F}$ ]) after dosing and clinical infection is suspected.

#### **7.2.6. Clinical Chemistry and Hematology**

Blood samples for biochemistry and hematology will be analyzed by local laboratories; see [Appendix 1](#) for a list of analytes to be analyzed.

#### **7.2.7. Archival Tumor Tissue**

##### ***7.2.7.1. Analysis of B7-H3***

Archival tumor tissue from primary tumor and/or from CNS/leptomeningeal metastasis (if available) obtained as standard of care at site should be sent to the central laboratory in the US for semi-quantitative immunohistochemistry analysis of B7-H3. The histological diagnosis will be confirmed. The analyses will be performed in batches. As per protocol version 8, this analysis will not be performed, and samples should no longer be shipped from sites.

At least 5 (preferably 10 to 15) formalin-fixed, paraffin-embedded slides of 3 to 5  $\mu\text{m}$  thickness (or a paraffin-embedded tissue block [enough for at least 5 sections]) will be needed. A detailed description of the procedures for sampling, handling, storage, and shipment of the samples will be provided by the central laboratory. Date of sampling, etc. will be recorded in the eCRF.

##### ***7.2.7.2. Analysis of Primary Tumor DNA (in case of separate Informed Consent)***

Archival tumor tissue from primary tumor (if available) obtained as standard of care at site should be sent to the central laboratory in the US for DNA sequencing and analysis for comparison with the ctDNA derived from the CSF. The analyses will be performed in batches. As per protocol version 8, this analysis will not be performed, and samples should no longer be shipped from sites.

At least 10 formalin-fixed, paraffin-embedded sections of 3 to 5  $\mu\text{m}$  thickness (or a paraffin-embedded tissue block [enough for at least 10 sections]) will be needed. If less than 10 are available, fewer sections are accepted. A detailed description of the procedures for sampling, handling, storage, and shipment of the samples will be provided by the central laboratory. Date of sampling, etc. will be recorded in the eCRF.

Upon issuance of the report, any leftover material will be discarded.

## 7.2.8. Immunogenicity

The presence of ADAs to Lu-DTPA-omburtamab in serum and CSF will be measured at the timepoints specified in the Schedule of Assessments ([Appendix 3](#)). No more than 2 mL of blood and 0.5 mL of CSF will be collected per timepoint, and sampling will be conducted conservatively given the age of the patients. Unscheduled sampling triggered by suspected immunologically related AEs may be conducted and collected until ADAs return to baseline. Dependent on the clinical data and occurrence of ADAs in Part 1, an assay to determine whether ADAs in CSF are neutralizing will be developed for Part 2. Samples will be stored frozen until testing at a central laboratory. ADAs will be evaluated using a validated enzyme-linked immunosorbent assay (ELISA) method.

## 7.2.9. Pharmacokinetic Analysis

To test the potential effect of ADAs on blood and CSF clearance of Lu-DTPA-omburtamab, PK exposure differences between Cycle 1 and Cycle 2 will be compared. Blood and CSF PK samples will be drawn at the following timepoints after the treatment doses in Cycle 1 and 2 ([Table 5](#)). No more than 2 mL of blood will be collected per timepoint and sampling. Samples will be stored frozen until testing at a central laboratory. Procedures for collection, processing, and shipping of PK blood and CSF samples will be detailed in a separate document.

Serum and CSF concentrations of Lu-DTPA-omburtamab will be determined using a validated analytical procedure. Specifics of the analytical method will be provided in a separate document.

**Table 5: Schedule for CSF and Blood Pharmacokinetic Sampling (Parts 1 and 2)**

Time of sampling following Cycle 1 Treatment Dose	Cycle 2 Treatment Dose
Baseline (prior to the treatment dose)	Baseline (prior to the treatment dose)
30 ( $\pm 10$ ) min 	30 ( $\pm 10$ ) min
1 h ( $\pm 10$ min)	1 h ( $\pm 10$ min)
4 h ( $\pm 10$ min)	4 h ( $\pm 10$ min)
24 ( $\pm 2$ ) h	24 ( $\pm 2$ ) h
48 ( $\pm 2$ ) h	48 ( $\pm 2$ ) h
7 ( $\pm 1$ ) days after (blood only) *,**	7 ( $\pm 1$ ) days after (blood only) *

\* Only drawn in Part 1; may be performed on Day 8; however, must be pre-dose.

\*\* In Part 1, Cycle 1, this is Day 15 as treatment dose is administered on Day 8.

 Both CSF and blood sampling; however, if both are not possible, CSF should be prioritized.

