#### 1.2.4. Preclinical Pharmacokinetics of Lu-DTPA-omburtamab

Electrochemiluminescence assays were developed and validated to support quantification of DTPA-omburtamab in plasma and CSF from cynomolgus monkey.

No standalone pharmacokinetic (PK) studies have been conducted with Lu-DTPA-omburtamab. Toxicokinetic parameters were determined in juvenile monkeys given a single intracerebroventricular infusion of vehicle or DTPA-omburtamab (CAR 1). The no-observed-adverse-effect level (NOAEL) of 1.5 mg/kg DTPA-omburtamab corresponded to a maximum observed drug concentration (Cmax) of 18,200 ng/mL total omburtamab and a mean area under the concentration-time curve (AUC) from time 0 to 672 hours of 1,350,000 hr·ng/mL and AUC from time 0 to infinity of 1,300,000 hr·ng/mL. There were no sex differences in toxicokinetic parameters. Total omburtamab was detectable in plasma at 1 hour post dose. Maximum plasma concentration and AUC increased with increasing dose in a greater than dose proportional manner. Time to maximum concentration was 12 hours and half-life was 23.9 to 26.1 hours. Mean clearance and volume of distribution of total omburtamab decreased with increasing dose. Total omburtamab was detectable in CSF in all dose groups at 24 hours post dose, and below the limit of quantification on Day 30. Concentrations were dose proportional for 0.1 and 0.75 mg/kg DTPA-omburtamab. There was no further increase in CSF levels at 24 hours post dose for 1.5 mg/kg compared to 0.75 mg/kg.

Biodistribution of Lu-DTPA-omburtamab (CAR 3.6 and 3) was evaluated in 2 studies with Sprague Dawley rats given a single intrathecal injection, and in 1 study with tumor-bearing athymic nude mice given a single IV injection of Lu-DTPA-omburtamab (CAR 3). The compound in these 3 studies was comparable to the clinical formulation (i.e., CAR  $\approx$  3).

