**Table 4: CSF and Blood Sampling and Scans in only Cycle 1 of Part 1**

Time point (after dosimetry dose)	CSF	Blood	Whole-body planar Gamma Camera Scan	SPECT a
Baseline	×	×		
30 ( $\pm 10$ ) min b	×	×		
1 h ( $\pm 10$ min)	×	×		
4 h ( $\pm 10$ min)	×	×	× (+ 1 h)	
24 ( $\pm 2$ ) h	×	×	× ( $\pm 2$ h)	× ( $\pm 2$ h)
48 ( $\pm 2$ ) h	×	×	× ( $\pm 2$ h)	
72 ( $\pm 4$ ) h	×	×		× ( $\pm 2$ h)
Day 5-7 c	×	×	×	×
Day 15 ( $\pm 12$ h) d	×	×	×	×

Abbreviations: CSF = cerebrospinal fluid.

a SPECT scan is optional.b Both CSF and blood sampling; however, if both are not possible, CSF should be prioritized.c Can be performed on Day 8; however, must be prior to the treatment dose.d To be performed 7 days ( $\pm 12$  h) after the treatment dose.

A dosimetry dose of 5 mCi was selected, with a possibility to increase to 10 mCi at the Sponsor's discretion in case of too low acquisition of radioactivity count.

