 Given 1-2 hours prior to IMP administration, including oral acetaminophen/paracetamol and antihistamine (e.g., diphenhydramine).

 Following the dosimetry dose, whole-body planar gamma camera scans will be performed at 4 h (4-5 h), 24 h (22-26 h), 48 h (46-50 h), and Day 5-7 (may be performed on Day 8; however, must prior to the treatment dose), and on Day 15 (±12 hours), i.e., 7 days after administration of the treatment dose (see [Table 4](#)). SPECT imaging is optional at 24 h (22-24 h), 72 h (70-74), Day 5-7 (or Day 8 pre-dose), and on Day 15 (±1) (i.e., 7 days after the treatment dose).

 Approximately 0.5 mL of CSF and 2 mL of peripheral blood will be drawn at each timepoint (see [Table 4](#)), i.e., before treatment (baseline; to avoid withdrawing too high volumes of CSF on the day of the dosimetry dose, baseline sample should be drawn in the time between placement of the ICV access device and 1 day before dosing) and following the dosimetry dose at 30 min (±5 min), 1 h (±10 min), 4 h (±10 min), 24 h (±30 min), 48 h (±1 h) and 72 h (±4 hour). In addition, samples are drawn on Day 5-7 (may be on Day 8; however, must be prior to the treatment dose) and on Day 15 (±12 hr), i.e., 7 days after administration of the treatment dose.

 In accordance with [Appendix 1](#).

 If CSF cytology sample is positive, it must be repeated within 4 weeks of the positive sampling.

 Drawn and held for culture only if elevated body temperature after dosing suggests infection rather than expected response to ICV dosing. Samples to be taken within 6 hours after completion of IMP infusion.

 The baseline ADA samples must be drawn prior to the dosimetry dose and to avoid withdrawing too high volumes of CSF on the day of the dosimetry dose, the samples should be drawn in the time between placement of the ICV access device and 1 day before dosing. Serum and CSF samples for ADA analyses will be drawn at baseline and after last treatment. Presence of ADA will be analyzed at a central laboratory.

 Blood and CSF samples for pharmacokinetics will be drawn as per [Table 5](#). On Day 15 (i.e., 7 days after the treatment dose), blood collection only.

 Pregnancy testing (serum or urine) is mandatory for women of childbearing potential at screening, within one week prior to each dose, and at the EOT Visit.

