 MRI of the brain and spine will be completed before first IMP administration, at the EOT Visit (preferably ±4 days of the actual visit date). MRI can be performed on a separate day to the other visit assessments, if required, in accordance with investigational site standards.

 Will be used to evaluate safety and efficacy.

 Beginning 24 hours before Lu-DTPA-omburtamab administration, divided into twice-daily doses for a total of 3 days.

 Given 1-2 hours prior to Lu-DTPA-omburtamab administration, including oral acetaminophen/paracetamol and antihistamine (e.g., diphenhydramine).

 In accordance with [Appendix 1](#).

 If CSF cytology sample is positive, it must be repeated within 4 weeks of the positive sampling.

 Drawn and held for culture only if elevated body temperature after dosing suggests infection rather than expected response to ICV dosing. Samples to be taken within 6 hours after completion of Lu-DTPA-omburtamab infusion.

 The ADA samples must be drawn prior to the Cycle 2 dose. The analysis can be performed from the samples drawn with the purpose of PK.

 Blood and CSF samples for pharmacokinetics will be drawn as per [Table 5](#). On Day 8, blood collection only.

 Pregnancy testing (serum or urine) is mandatory for women of childbearing potential at screening, within one week prior to each dose, and at the EOT Visit.

 Non-serious AEs should be reported from the day of first IMP administration until 5 weeks after the patient's last dose of IMP. Non-serious AEs occurring between signing the ICF and the first IMP administration must be recorded as medical history. Serious AEs should be reported from signing the ICF until 5 weeks after the patient's last dose of IMP.

Thereafter and during the follow-up period, only SAEs or Grade 3 or higher AEs at least possibly related to Lu-DTPA-omburtamab or to the presence of the indwelling catheter system should be reported until end of trial. During the post-trial monitoring period, new onset of cancers, regardless of causality, should be reported.

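### Table 5 footnote * misdates the 7-day serum PK sample: a Day 8 pre-dose draw precedes the treatment dose in Part 1 Cycle 1, and in Cycle 2 there is no Day 8 dose

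*Combined protocol and SAP*

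**What the plan says.** Section 7.2.9 times the PK samples from the treatment doses in Cycles 1 and 2. The last row of Table 5 is a blood-only sample 7 (±1) days after the dose, marked with footnote * in both cycle columns: "Only drawn in Part 1; may be performed on Day 8; however, must be pre-dose".

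The other statements about this sample are:

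- Table 5 footnote **, on the Cycle 1 cell only: "In Part 1, Cycle 1, this is Day 15 as treatment dose is administered on Day 8".
- Table 6 (Part 1 Cycle 1) marks PK sampling under Day 8 and Day 15. Its footnote 18 adds: "On Day 15 (i.e., 7 days after the treatment dose), blood collection only".
- Table 7 (Part 1 Cycle 2) footnote 14: "On Day 8, blood collection only". It sets no pre-dose condition.

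Nearly the same wording appears in Table 4 footnote c, for the Day 5-7 absorbed-dose sample: "Can be performed on Day 8; however, must be prior to the treatment dose".

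On use of the data, section 7.2.9 says that "PK exposure differences between Cycle 1 and Cycle 2 will be compared", in order to look for an effect of anti-drug antibodies (ADA) on clearance. Section 8.8 plans Cmax, AUC and half-life by noncompartmental methods.

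**The concern.** Footnote * permits a draw that cannot be the sample its row describes. The Cycle 1 cell carries two incompatible instructions: Day 8 before the dose, and Day 15. The clause is correct in Table 4, where the sample follows the Day 1 dosimetry dose. It looks carried over from there, although that is an inference.

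The 7-day draw is the only scheduled serum PK sample after 48 h in Part 1 Cycle 1. Table 6 already marks Day 8 as a PK day, so a site could take the pre-dose tube as meeting the 7-day requirement. That patient would have two baselines and no late sample, and the missed time point could not be recovered. The terminal half-life and extrapolated AUC would be weakened in one of the two cycles to be compared.

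A lesser mismatch of the same kind affects the absorbed-dose samples. Table 4 and Table 6 footnote 13 give different time windows for the same draws.

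**Working it through.** **Calendar day of the sample.** Sample day = treatment-dose day + 7, with a window of ±1 day.

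| | Treatment dose | Nominal day | Window | Day 8 pre-dose draw under footnote * |
|---|---|---|---|---|
| Part 1 Cycle 1 | Day 8 | 8 + 7 = 15 | Day 14-16 | Before the dose; same as the baseline row |
| Part 1 Cycle 2 | Day 1 | 1 + 7 = 8 | Day 7-9 | Right day, but no dose that day |

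This reproduces the Day 15 in footnote ** and in Table 6, and the Day 8 in Table 7. Section 3.1.1 allows at most two cycles in Part 1, so no later dose gives the pre-dose condition a meaning in Cycle 2. Part 2 does not take this sample. Footnote * therefore works in neither cycle to which it applies.

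**Effect on one patient if footnote * is followed in Cycle 1.** The scheduled post-dose serum times are 0.5, 1, 4, 24, 48 and 168 h; losing the last leaves 48 h as the final time. After a 12 h peak, the remaining points fall from three (24, 48, 168 h) to two. A log-linear slope through two points leaves no residual degree of freedom.

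**Illustrative share of AUC beyond the last sample.** The protocol gives no human half-life. Section 1.2.4 reports for juvenile monkeys: "Time to maximum concentration was 12 hours and half-life was 23.9 to 26.1 hours". The illustration assumes one compartment with first-order input:

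- ke = ln 2 / half-life
- ka solves ln(ka/ke)/(ka − ke) = 12 h
- share beyond t = ka/(ka − ke) × [exp(−ke·t) − (ke/ka)·exp(−ka·t)]

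For a half-life of 23.9 h, ke = 0.693/23.9 = 0.0290 per h and ka = 0.182 per h, so ka/(ka − ke) = 0.182/0.153 = 1.19. At 48 h, exp(−1.392) = 0.249 and the second term is negligible, giving 1.19 × 0.249 = 29.6%. At 168 h, exp(−4.872) = 0.0077, giving 0.9%.

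| Half-life | Source | Beyond 48 h | Beyond 168 h |
|---|---|---|---|
| 23.9 h | monkey | 29.6% | 0.9% |
| 26.1 h | monkey | 32.5% | 1.3% |
| 48 h | assumed | 53.0% | 9.4% |
| 72 h | assumed | 65.1% | 20.5% |

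**Absorbed-dose windows.**

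| Time | Table 4 | Table 6 footnote 13 | Ratio |
|---|---|---|---|
| 30 min | ±10 min | ±5 min | 10/5 = 2 |
| 24 h | ±2 h | ±30 min | 120/30 = 4 |
| 48 h | ±2 h | ±1 h | 2/1 = 2 |

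A 24 h draw taken one hour late is on time under Table 4 and late under footnote 13.

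**The case against.** The best defence is that the intended day is easy to recover. The column heading, the row label, footnote ** on the same cell, the Table 6 grid and Table 6 footnote 18 all point to a post-dose sample on Day 15, and footnote * only permits the Day 8 draw. Part 1 patients are also on site with blood being taken on Day 15, because Table 4 requires an absorbed-dose sample then, so a missed PK tube is less likely. That sample measures lutetium-177 activity in blood, so some late clearance information would survive. Part 2 stops PK sampling at 48 h by design and is analysed by the same noncompartmental methods. A Part 1 patient without the 7-day sample would simply have the Part 2 serum schedule.

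These points limit the consequence and are accepted. They do not make the footnote correct. The activity count is not the serum assay. The short Part 2 schedule also means that the Part 1 7-day draw is the trial's only late serum PK sample, which is a reason to protect it.

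The AUC figures deserve caution too. They rest on monkey plasma values for total omburtamab after DTPA-omburtamab with a chelator-to-antibody ratio of 1, whereas the clinical product has a ratio of 3. They also rest on two assumed half-lives and a chosen model. They illustrate one misread case and do not estimate an effect on the trial.

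On the windows, the footnote 13 limits lie inside those of Table 4, so a site using the narrower set complies with both.

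**Conclusion.** Footnote * is wrong as written. In Part 1 Cycle 1 it allows a second baseline in place of the 7-day sample; in Cycle 2 its pre-dose condition is empty, though no sample is lost there. This is an internal inconsistency. The intended design, a sample 7 days after each Part 1 treatment dose, is not in dispute.

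The importance is low. Harm requires a site to act on footnote * against the other statements. No primary endpoint, dose decision or safety rule depends on it. CSF PK is untouched because the row is blood only, and Cmax and the 0-48 h AUC stay comparable between cycles. For a patient sampled under footnote *, follow-up of serum concentration shrinks from 168 h to 48 h. The unobserved share of AUC would be about 30% to 32% on the monkey half-lives, and 53% to 65% if the human half-life were 48 to 72 h, which is an assumption.

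The absorbed-dose window mismatch is real but secondary. It decides only whether a sample counts as on time.

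**What to change.** Reduce footnote * to the statement that the sample is drawn in Part 1 only. Extend footnote ** to both columns, giving Day 15 for Part 1 Cycle 1 and Day 8 for Part 1 Cycle 2.

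Separately, use one set of absorbed-dose sampling windows in Table 4 and Table 6 footnote 13. The sponsor should choose according to what the dosimetry calculation needs and what sites can achieve; until then, the narrower set satisfies both texts.

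The cost is footnote and table wording, with no added visit, sample or patient burden.

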## 7.3. Efficacy Assessments

### 7.3.1. Progression-free Survival

Progression-free survival (PFS) will be assessed by MRI, neurological examination, and CSF cytology. As detailed in the RAPNO criteria ([Appendix 6](#)), progression is defined when any of the PD criteria are met. The timeframe for assessment of PFS will be from the first treatment dose of Lu-DTPA-omburtamab to time of disease progression or death from any cause. Patients lost to follow-up without any sign of progression will be censored at the date of last PFS assessment.

### 7.3.2. Response Evaluation, Overall Response Rate, and Duration of Response

Response, as defined by the RAPNO criteria (Warren et al. 2018; see Appendix 6) will be assessed in Part 1 at the EOT Visit. In Part 2, response will be assessed at end of Cycle 1 and Cycle 3, EOT Visit, then 26, 39, and 52 weeks post first dose, followed by 78 and 104 weeks post first dose of Lu-DTPA-omburtamab. Notably, objective response and stable disease requires that all criteria are met, while progression is defined when any of the PD criteria are met.

The ORR will be calculated from baseline MRI scans and from scans after the dosing of Lu-DTPA-omburtamab using 2 methods: firstly, by considering MRI data, neurological examination, and CSF cytology data together (RAPNO criteria); secondly, by considering CSF cytology data only. ORR will be defined as the proportion of all evaluable patients achieving a CR or PR as best overall response at the time of assessment.

Investigator-assessed DoR (Part 2) is defined as the time from response (CR or PR) to progression. Patients without any sign of progression will be censored at the date of their last PFS assessment.

In Part 1 and Part 2, the baseline CSF cytology assessment must be completed within 3 weeks prior to the first Lu-DTPA-omburtamab treatment dose infusion. Cerebrospinal fluid cytology should be assessed as positive/negative. Cerebrospinal fluid cytology will be assessed in Part 1 at screening, the EOT Visit, and in Part 2 at screening, end of Cycle 1 and Cycle 3, EOT Visit, and at each Follow-up Visit.

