##### **4.3.2. End of Treatment**

The end of treatment (EOT) is defined as the day the last dose of Lu-DTPA-omburtamab is received. The EOT Visit should occur 5 to 6 weeks after the last dose, whether this is a premature treatment discontinuation or treatment completion.

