 The Lu-DTPA-omburtamab Treatment Period is divided into 5-week cycles. In Part 2, a cycle consists of a treatment dose on Day 1. The patient can receive up to 5 cycles at the discretion of the investigator. The infusion reservoir must be flushed with HSA and CSF after each infusion. The patient will be observed post treatment to decide if further cycles can be administered.

Day 1, 15, and 29 for Cycles 2 to 5 correspond to Day 36, 50, and 64 (for Cycle 2), Day 71, 85, 99 (for Cycle 3), 106, 120, 134 (for Cycle 4), and 141, 155, and 169 (for Cycle 5). Adjustments to the dosing schedule will be accommodated on a patient-by-patient basis depending on the clinical condition of the patient.

 If the IMP is discontinued prior to completion of all scheduled visits of the cycle (i.e., up to and including Day 29), the treatment visits that fall after the date of the EOT Visit should be skipped, and the patient should move directly into the follow-up phase. If the IMP is discontinued after Cycle 1, an unscheduled visit (including MRI etc.) should be done at 13 weeks post first dose.

 All patients who are dosed with Lu-DTPA-omburtamab in Part 2 should be followed up regularly (every 13 [±2] weeks, i.e., 26, 39, and 52 weeks post first dose, then every 26 [±2] weeks, i.e., 78 and 104 weeks post first dose, and thereafter annually) for monitoring of secondary malignancies during the trial and for at least 10 years after the end of trial, or until death, if sooner.

 Informed consent must be obtained before any trial-related procedures. If the indwelling ICV access device (e.g., Ommaya) is placed in connection with the tumor resection, the informed consent must be obtained prior to the surgery, and before the start of the screening period, unless this is placed as part of a standard of care procedure at site. If any procedures/tests are from before informed consent is obtained, it must be clear from source documents that this was not performed for the purpose of the present trial. In these cases, the procedures/tests do not need to be repeated at the Screening Visit if they were performed within the allowed timelines. The investigator is responsible for documenting this properly.

 Only anti-cancer therapy.

 Physical examinations to be performed at screening and as clinically indicated.

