## Appendix 6: Assessment in Pediatric Neuro-oncology (RAPNO) Criteria

Response definitions: patients must meet **ALL** criteria in each response/stable disease category, or **ANY** criteria in the progressive disease category

	Complete Response (CR)	Partial Response (PR)	Stable Disease	Progressive Disease (PD)
Criteria	Must meet ALL criteria	Must meet ALL criteria	Must meet ALL criteria	Must meet ANY criteria
MRI-brain	Complete disappearance of all disease (enhancing and non-enhancing, measurable and nonmeasurable) for a minimum of 4 weeks; no new lesions	≥50% decrease (compared with baseline) in the sum of the products of perpendicular diameters of all (up to 4) measurable lesions sustained for at least 4 weeks; no progression of nonmeasurable disease	Does not meet criteria for CR, PR, or PD	≥25% increase (compared with smallest measurement at any timepoint) in the sum of the products of perpendicular diameters of all measurable lesions; significant progression of nonmeasurable disease not attributed to prior therapy; any new tumor (any new lesions suspected to be treatment related should be confirmed by biopsy)
MRI-spine	Complete disappearance of all disease (enhancing and non-enhancing, measurable and nonmeasurable) for a minimum of 4 weeks; no new lesions	≥50% decrease (compared with baseline) in the sum of the products of perpendicular diameters of all measurable lesions sustained for at least 4 weeks; no progression of nonmeasurable disease. If negative at baseline, must remain negative	Does not meet criteria for CR, PR, or PD	≥25% increase (compared with smallest tumor measurement at any timepoint) in the sum of the products of perpendicular diameters of all (up to 4) measurable lesions; significant progression of nonmeasurable disease not attributed to prior therapy; any new tumor (any new lesions suspected to be treatment related should be confirmed by biopsy)
CSF cytology	If tumor cells are present at baseline, must be negative × 2 (sampling at least 2 weeks apart)	If absent (negative) at baseline, must remain absent. If present at baseline, can be present or absent	If absent at baseline, must remain absent. If present at baseline, can be present or absent	Previously absent tumor cells in CSF now present (positive)
Neurologic exam a	Stable or improving	Stable or improving	Stable or improving	Clinical deterioration not attributable to other causes

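### RAPNO response must last 4 weeks, but Part 1 has one post-baseline MRI, and for on-schedule five-cycle patients in Part 2 the EOT and week-26 MRIs nearly coincide and do not reliably confirm each other

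*Combined protocol and SAP*

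**What the plan says.** **Response definition.** In Appendix 6 the MRI criterion for CR is disappearance of all disease ("measurable and nonmeasurable) for a minimum of 4 weeks; no new lesions"), and PR requires the 50% decrease to be "sustained for at least 4 weeks". If tumor cells were present in CSF at baseline, CR also needs two negative cytology samples at least 2 weeks apart. Section 7.3.2 requires all criteria to be met.

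**Part 1.** Section 7.3.2 says RAPNO response "will be assessed in Part 1 at the EOT Visit". Table 7, footnote 6, sets the imaging: "MRI of the brain and spine will be completed before first IMP administration, at the EOT Visit". Cytology is likewise scheduled at screening and EOT only, and Table 7 labels EOT as also the end of trial.

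**Part 2.** Section 7.3.2: "In Part 2, response will be assessed at end of Cycle 1 and Cycle 3, EOT Visit, then 26, 39, and 52 weeks", followed by weeks 78 and 104. Section 4.3.2: "The EOT Visit should occur 5 to 6 weeks after the last dose". The follow-up visits are counted from first dose, with a window of ±2 weeks (Table 8). Table 8, footnote 10, lets the MRI be done on another day: preferably within ±4 days of the EOT visit, and within ±2 weeks of a follow-up visit.

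**Related rules.** Section 2.2.2.2 defines ORR as best overall response across the Part 2 assessments. Section 6.1 allows additional anti-cancer treatment after the EOT visit. Neither Section 7.3.2 nor Section 8.4.1 names a confirming scan or says how an unconfirmed response counts.

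**The concern.** A response defined by duration needs two assessments far enough apart to show it. Part 1 schedules only one after baseline.

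In Part 2, EOT is counted from the last dose and week 26 from the first dose. After five 5-week cycles the two arrive at almost the same date. EOT is the first response assessment since the end of Cycle 3, so it is where a response to the full course would first be seen. The visit that follows on the schedule is too close to confirm it, and the next one is about three months away.

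At stake is ORR, and the DoR that starts from it. A patient whose response began by EOT and lasted 4 to 13 weeks would meet Appendix 6, yet the scheduled scans might not show it. Such a patient also has two brain and spine MRIs, sedated if necessary (Section 7.2.3), and two reservoir CSF samples within about a week.

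**Working it through.** **Inputs.** Cycle length is 35 days. EOT is 35-42 days after the last dose (Section 4.3.2). Follow-up visits are at weeks 26, 39 and 52 after first dose, ±14 days (Table 8). The required MRI duration is 28 days (Appendix 6).

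**Reproducing the plan's calendar.** Day 1 of cycle c = 1 + 35(c − 1), which gives Days 1, 36, 71, 106 and 141. Adding 28 gives the end-of-cycle visits: Days 29, 64, 99, 134 and 169. Table 8, footnote 1, lists the Cycle 5 days as "141, 155, and 169 (for Cycle 5"), so the calendar agrees.

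**EOT and week 26, five cycles, no delay.**
- EOT = 141 + 35 to 141 + 42 = Day 176-183.
- Week 26 = 1 + 7 × 26 = Day 183, visit window Day 169-197.
- Nominal gap: 183 − 183 = 0 to 183 − 176 = 7 days.
- Largest gap by visit windows: 197 − 176 = 21 days.
- EOT MRI 4 days early and week-26 MRI on Day 197: 197 − 172 = 25 days.
- Week-26 visit 14 days late and its MRI a further 14 days late: 211 − 172 = 39 days. Only this stacking reaches 28.

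**Other consecutive Part 2 assessments, five cycles.**

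| Pair | Gap (days) |
|---|---|
| End of Cycle 1 (Day 29) to end of Cycle 3 (Day 99) | 70 |
| End of Cycle 3 (Day 99) to EOT (Day 176-183) | 77-84 |
| EOT (Day 176-183) to week 39 (Day 274) | 91-98 |
| Week 26 (Day 183) to week 39 (Day 274) | 91 |

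All of these exceed 28 days, so the EOT/week-26 pair is the exception.

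**Who is affected.** After four cycles, EOT is Day 106 + 35 to 42 = Day 141-148, and week 26 is 35-42 days later, which is enough. With five cycles and cumulative delay, EOT moves past week 26. At 4 weeks of delay EOT is Day 204-211 (21-28 days after Day 183), and at 5 weeks it is Day 211-218 (28-35 days after). The overlap therefore fades at about 4 to 5 weeks of delay.

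**Cytology.** The gap needed is 14 days, and only if baseline was positive. Nominal dates (0-7 days) do not give it. The visit windows can: 197 − 183 = 14 and 197 − 176 = 21 days.

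**Part 1.** EOT is Day 71-78 after two cycles (last dose Day 36), or Day 43-50 if only Cycle 1 is given (last dose Day 8). Either way there is one post-baseline MRI and one scheduled post-baseline cytology. The repeat-sample footnotes in Tables 6 and 7 apply to positive samples, not to the second negative that CR may need.

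**Size per patient.** With the planned 20 evaluable patients (Section 8.1), one response is 1/20 = 5 percentage points of ORR.

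**The case against.** The strongest reply is that the schedule as a whole can confirm responses. A reader might infer from the overlap that Part 2 ORR cannot be confirmed at all. The table of gaps shows otherwise: a response first seen at the end of Cycle 1 or Cycle 3 is confirmable at the next scheduled scan, and a long enough one first seen at EOT is confirmable at week 39. Intervals of 70 days or more elsewhere also miss short responses, so that loss is not unique to EOT.

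Three other strong readings also fail:
- *EOT and week 26 can never be 28 days apart.* Stacked MRI windows reach 39 days, and the EOT window is only a preference. Nothing directs sites to use the windows this way, so the pair is unreliable rather than impossible.
- *The second CSF sample adds nothing.* Two negatives 14 days apart can fit the visit windows, and cytology-only ORR is a planned analysis.
- *Part 1 results are biased to zero responders.* Section 2.2.2.1 lists activity, dosimetry and PK as the Part 1 secondary endpoints, Section 8.4.1 covers Part 2 only, and no pooling is planned. Stable and progressive disease carry no 4-week rule and can still be recorded.

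The number of affected patients is also unknown. Delays of up to 8 weeks are allowed (Section 5.3.1), and the DMC may find five cycles infeasible (Section 4.4).

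What stands is narrower. Patients on the protocol's own five-cycle calendar get two nearly simultaneous assessments, then wait about 13 weeks for a scan that can confirm an EOT response, with other therapy permitted in between.

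**Conclusion.** The point holds in limited form. For patients completing five cycles with little or no delay, the EOT and week-26 MRIs are largely redundant: 0-7 days apart nominally and at most 21 by visit windows, against 28 required. A response first seen at EOT has no reliable confirming scan for 91-98 days, so one lasting 4 to 13 weeks may be missed, at 5 points of ORR each. In Part 1, RAPNO CR or PR as defined cannot be shown from the scheduled assessments, which conflicts with Section 7.3.2 but touches no listed endpoint.

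This assumes dosing on the Table 8 days, EOT at 5 to 6 weeks, and MRI windows that are not stacked. How many patients will follow that course, or respond first at EOT, cannot be derived from the documents. ORR is a secondary, descriptive endpoint, so the point is moderate. It is worth acting on because the correction is cheap.

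**What to change.** **1. Table 8 (new footnote) and Section 7.3.2, Part 2.** When the EOT MRI falls on the week-26 visit date or less than 28 days before it, EOT serves as the week-26 time point. The week-26 MRI and CSF assessment is then done at least 28 days after the EOT MRI. For an undelayed five-cycle patient this is 176 + 28 = Day 204 to 183 + 28 = Day 211, or later, as an allowed exception to the ±2-week window. When week 26 precedes EOT, leave it unchanged, so that progression assessment is not postponed in dose-delayed patients. Record any anti-cancer therapy started before the moved scan, and do not count a scan taken after such therapy as confirming a response.

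**2. Section 7.3.2, Part 1.** List EOT tumor findings as unconfirmed change rather than RAPNO CR or PR. Stable and progressive disease can still be reported.

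**Cost.** One footnote and a few sentences, with no added scans. One follow-up assessment moves 21-28 days later (from Day 183 to Day 204-211) for these patients. Because EOT stands in at week 26, progression is still assessed there, and the interval from the moved scan to week 39 is 274 − 211 = 63 to 274 − 204 = 70 days. The wait to confirm an EOT response falls from about 13 weeks to about 4. The overlap remains where a short delay puts week 26 just before EOT.
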